1.0 Objectives

1.1 Primary objective

- To investigate the risk of hip fracture in occasional meat-eaters, pescatarians, and vegetarians compared to regular meat-eaters.

1.2 Secondary objectives

- To determine the roles of potential modifying factors on associations between each diet group and hip fracture risk, including age, sex, body mass index (BMI), and adherence to the Alternative Healthy Eating Index (AHEI).
- To investigate interactions between diet groups and genotypes on bone mineral density (BMD) and hip fracture risk.
- To determine the roles of potential mediating factors on any observed associations between diet groups and hip fracture risk, including the roles of BMI, measures of body composition measures, circulating levels of vitamin D and IGF-1, and dietary intake of protein, calcium, vitamin B12, and omega-3 fatty acids.

2.0 Study design

The dataset will use participant data from the pre-existing UK Biobank database. This is a prospective cohort of over 500,000 adults across England, Scotland, and Wales, aged 40 – 69 years at recruitment in 2006-2010. Participants were recruited via National Health Service (NHS) patient registers, and attended one of 22 assessment centres across the UK, where participants were asked to complete a touchscreen questionnaire, verbal interview, physical measures, and a biosample collection (more information available at [UK Biobank - UK Biobank](#)).

3.0 Data cleaning

3.1 Exclusion criteria

Participants will be excluded from all analyses for any of the following reasons:

- Unable to link dietary and lifestyle data with hospital data (e.g. no NHS number provided and unable to match with records).
- Had a hip fracture (World Health Organisation, WHO International Classification of Disease (ICD-10) codes S72.0-S72.2) or osteoporosis (ICD-10 codes M80-M82) before or on the date of recruitment.

- Outlier diet or anthropometric data (energy intake < 500 or > 5000 kcal/day or BMI < 10 or > 60 kg/m²)
- Withdrew consent during the study period.
- Biological sex assigned at birth differed to self-reported sex at recruitment.
- Unable to be classified into a diet group (e.g. responded “do not know” or “prefer not to say” for questions on meat or fish intake).

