5.0 Outcomes

The primary outcome will be first incidence of hip fracture (ICD-9 code 820 and ICD-10 codes S72.0-S72.2) identified using hospital inpatient data for England, Scotland, and Wales. This includes Hospital Episode Statistics for England until 30th September 2021, Scottish Morbidity Records for Scotland until 31st July 2021, and the Patient Episode Database for Wales until 28th Feb 2018. The timeframe will be person-years until hip fracture incidence, or until end of study period or death in non-cases, calculated as age at time of event or censoring minus age at study entry. Sources and dates of availability for each region’s hospital inpatient data (and therefore censoring dates) are presented in Table 2.

Table 2: Hospital inpatient data in England, Scotland, and Wales.

Country	Data source	Period of time for which data is available
England	Hospital Episode Statistics (HES)	1997 – 30 th Sept 2021
Scotland	Scottish Morbidity Record (SMR)	1981 – 31 st July 2021
Wales	Patient Episode Database for Wales (PEDW)	1998 – 28 th Feb 2018

Adapted from: [External Info : Data providers and dates \(ox.ac.uk\)](#)

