11.1.4 Other

Number of children

At recruitment in the touchscreen questionnaire, women were asked “how many children have you given birth to?”. This will be treated as a continuous variable. This variable is not applicable to men.

Menopausal status

At recruitment in the touchscreen questionnaire, women were asked multiple questions relating to menopausal status. Women will be defined as premenopausal or postmenopausal at recruitment using the following criteria:

Premenopausal: answered “no” to the question that asked about having gone through menopause, or answered “not sure”, and:

- Were < 55 years old, did not report having a bilateral oophorectomy or hysterectomy, and did not report using hormone replacement therapy (HRT), or
- Were < 55 years old, did not report having a bilateral oophorectomy or hysterectomy, and reported menstruating on the day of recruitment

Postmenopausal: answered “yes” to having gone through menopause, or answered “not sure” and were ≥ 55 years old or had a bilateral oophorectomy.

Menopausal hormone replacement therapy (HRT)

At recruitment in the touchscreen questionnaire, women were asked “Have you ever used hormone replacement therapy?” and if yes, “How old were you when you last used hormone replacement therapy?”. We will categorise HRT use based on these questions as “Current”, “Former”, “Never”, or “Unknown”.

Chronic disease prevalence at recruitment

We will identify prevalence of chronic diseases that could act as confounders using both self-reported information from questions on health and medical history asked in the touchscreen questionnaire, and through use of hospital records (with the date of diagnosis being before or on the date of recruitment). Relevant chronic diseases that will be considered confounders will be informed by existing literature and by use of a Directed Acyclic Graph (DAG), but will likely include hip fracture, other fracture, osteoporosis, diabetes, cardiovascular disease, and cancer.

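### Prior hip fracture is excluded by ICD-10 codes only, although ICD-9 820 is in the first-incidence outcome and prior hip fracture and osteoporosis are likely covariates

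*SAP*

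**What the plan says.** Three sections of the SAP define or use prior disease.

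- **Section 3.1 (exclusions from all analyses).** The hip fracture criterion reads "Had a hip fracture (World Health Organisation, WHO International Classification of Disease (ICD-10) codes S72.0-S72.2", and the sentence goes on "or osteoporosis (ICD-10 codes M80-M82) before or on the date of recruitment". No ICD-9 code and no self-report is mentioned.
- **Section 5.0 (primary outcome).** The outcome is "first incidence of hip fracture (ICD-9 code 820 and ICD-10 codes S72.0-S72.2) identified using hospital inpatient data". Follow-up time is age at event or censoring less age at entry. Table 2 gives the period of hospital data for England as "1997 – 30 th Sept 2021"; records start in 1981 for Scotland and in 1998 for Wales.
- **Section 11.1.4 (chronic disease covariates).** Prevalent disease is to be found "using both self-reported information from questions on health and medical history asked in the touchscreen questionnaire, and through use of hospital records". The diseases treated as confounders depend on the literature and a DAG, "but will likely include hip fracture, other fracture, osteoporosis, diabetes, cardiovascular disease, and cancer".

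Section 2.0 fixes the start of follow-up: participants were "aged 40 – 69 years at recruitment in 2006-2010".

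**The concern.** In a first-incidence cohort, the codes that define the event should also define the prior event that makes a person ineligible. Here they differ by one code, and that code belongs to the older classification, which is the one most likely to mark fractures before entry.

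Separately, a condition that removes a person from every analysis cannot vary among those who remain, so it cannot serve as a covariate. The entry in section 11.1.4 has a function only if some people with prior hip fracture or osteoporosis are still in the cohort.

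Two things are at stake. Two analysts following the SAP could build different cohorts. And some people with a previous fracture or known osteoporosis could stay in, although the exclusion appears meant to remove them. They plausibly have a higher fracture risk and may have changed diet because of their condition.

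**Working it through.** The SAP gives no figure on this point, so the check is mainly a comparison of definitions. Table 3 is used only at the end, for scale.

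**1. Definitions side by side**

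| SAP section | Use | Hip fracture | Osteoporosis |
|---|---|---|---|
| 3.1 | Exclusion | ICD-10 S72.0-S72.2 | ICD-10 M80-M82 |
| 5.0 | Outcome | ICD-9 820, ICD-10 S72.0-S72.2 | not applicable |
| 11.1.4 | Likely covariate | Self-report or hospital record | Self-report or hospital record |

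ICD-9 820 is in the outcome but not in the exclusion. Self-report is a source for covariates but not for the exclusion.

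**2. When an ICD-9 820 record can arise**

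Years of hospital data before entry (recruitment year minus first year in Table 2):

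- Scotland: 2006 − 1981 = 25 to 2010 − 1981 = 29
- England: 2006 − 1997 = 9 to 2010 − 1997 = 13
- Wales: 2006 − 1998 = 8 to 2010 − 1998 = 12

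The SAP does not date the change from ICD-9 to ICD-10. If ICD-9 appears only in older records, code 820 can mark only fractures before entry, and mainly in Scotland.

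**3. One participant under the rules as written**

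Take a participant with an ICD-9 820 record before recruitment and no S72 or M80-M82 code by that date. Section 3.1 does not exclude them. Section 5.0 then allows two readings:

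- The earliest record sets the event date. Age at event is below age at entry, so follow-up is negative. The record might then drop out of the analysis, but the SAP does not say so.
- Only records after entry count. A later fracture is then scored as the first.

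**4. Section 11.1.4 against section 3.1**

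People with an ICD-10 hospital code are already out. Those who could still carry a prior hip fracture or osteoporosis as a covariate are the ones found only by self-report or only by ICD-9. The covariate entry therefore implies that they remain.

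**5. Scale**

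- *ICD-9 part.* Scottish centres are 2 of 22 (section 11.1.1). In 1981 participants were between 40 − 29 = 11 and 69 − 25 = 44 years old. Few hip fractures are likely in that age range.
- *All missed prior cases, by assumption.* Let a share q of the 472,337 participants be missed prior cases with r times the fracture rate of the rest. Their share of events is qr / (1 − q + qr). The SAP's 3% incidence gives 0.03 × 472,337 ≈ 14,170 events.
  - q = 0.1%, r = 2: 472 people, 0.002 / 1.001 = 0.2%, about 28 events.
  - q = 1%, r = 5: 4,723 people, 0.05 / 1.04 = 4.8%, about 681 events.
- *Effect on Table 3.* The minimum detectable HR is exp[(1.960 + 0.842) / (SD × √events)], with SD = √[p(1 − p)] and events equal to 3% of the diet group plus regular meat-eaters.
  - Pescatarian: p = 10,696 / 258,267 = 0.0414, SD = 0.199, events = 7,748, HR = 1.173 (stated 1.17).
  - Vegetarian: p = 8,685 / 256,256 = 0.0339, SD = 0.181, events = 7,688, HR = 1.193 (stated 1.19).
  - Losing 5% of events moves these to 1.178 and 1.199.

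The cost in precision is negligible over this range. The range says nothing about bias, for which the SAP gives no basis.

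**The case against.** The best case for leaving the text alone has four parts.

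- **The ICD-9 limb depends on a date the SAP does not give.** This is true of the claim that code 820 does no valid work in the outcome. It is not true of the mismatch: if ICD-9 codes were still used after recruitment, the exclusion list would be just as incomplete.
- **Code 820 in a first-incidence definition may be there to recognise earlier fractures.** That is possible, but the SAP does not say so, and section 3.1 is where such a rule belongs.
- **Excluding on hospital codes and adjusting for self-reported history can be a coherent design.** This also stands in part. If it is the intention, the SAP must say which cases remain. Section 11.1.4 does not; it also draws on hospital records for the same covariates.
- **Section 8.4 plans related sensitivity analyses.** Dropping cases in the first three years leaves prior-fracture participants whose later events fall after that point. Dropping people on long-term treatment does not define the main cohort. Adjusting for region removes no prior cases.

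A reader might also infer more than the documents support.

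- *That the current rule acts unevenly because Scotland has a 25-29 year look-back.* Under an ICD-10-only rule, and on the same assumption about older records, the effective Scottish look-back starts when ICD-10 coding began, not in 1981. Adding ICD-9 is what would lengthen it.
- *That all these people are misallocated under the stated rule.* The rule is code-based, and someone with only a self-report is handled as it says.
- *That the adjustment set is fixed.* Section 11.1.4 is worded as likely and depends on a DAG.
- *That retained osteoporosis cases breach first incidence.* They are not prior hip fractures. They bear only on the purpose of the exclusion.

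**Conclusion.** The point holds as an inconsistency in how the cohort is defined. The exclusion and the outcome use different hip fracture code lists, and section 11.1.4 lists as likely covariates two conditions that section 3.1 excludes from all analyses. As written, participants with a pre-recruitment ICD-9 820 record are not excluded, and their events have no valid handling. Prior cases known only by self-report also appear to remain.

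The number affected cannot be derived from the SAP. The ICD-9 part is probably small and mainly Scottish, assuming that ICD-9 appears only in older records. The self-report part could arise in all three countries and its size is unknown. The loss of power from removing these people would be trivial over the assumed range. What needs correcting is the cohort definition and its reproducibility, with some possible reverse causation. It should be corrected because the correction is specific and cheap.

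**What to change.** 1. In section 3.1, add ICD-9 820 and the matching ICD-9 osteoporosis code to the exclusion.
2. In section 5.0, restrict the outcome to events after the recruitment date. ICD-9 820 then has no role there unless the sponsor shows that such codes occur during follow-up.
3. Apply the self-reported history already used in section 11.1.4 to the same exclusion, at least as a sensitivity analysis. The SAP should state whether self-report identifies fracture site; if it does not, say how hip fracture is told apart from other fracture.
4. Remove hip fracture and osteoporosis from the covariate list for any cohort that excludes them. If self-report-only cases stay in the main cohort, say so and name the covariate accordingly.

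The cost is an edit to code lists, using data the SAP already plans to use, and a small loss of participants. Adding ICD-9 also makes the effective look-back longer in Scotland (up to 25-29 years) than in England (9-13) and Wales (8-12). Using self-report in the exclusion evens this out in part.

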4.0 Exposures

4.1 Primary exposure

The primary exposure of interest will be diet group (regular meat-eater, occasional meat-eater, pescatarian, or vegetarian) – definitions for each diet group are given in Table 1. Due to the small number of vegans in the UK Biobank reported in previous studies (1, 2), vegans will be combined with the vegetarian group for main analyses, and will be considered separately in sensitivity analyses.

Table 1: Diet group categories and definitions.

Diet group	Definition
Regular meat-eater	Total meat intake ≥ 5 servings/week
Occasional meat-eater	Total meat intake < 5 servings /week & > once/month
Pescatarian	Total meat intake ≤ once/month & total fish intake > once/month
Vegetarian	Total meat and fish intakes ≤ once/month, intake of any dairy products or eggs > once/month
Vegan	Total meat, total fish, dairy products, and eggs intake ≤ once/month

4.2 Exposure assessment

Participants will be classified into diet groups based on responses to questions in the touchscreen food frequency questionnaire (FFQ) completed at recruitment that relate to meat, fish, eggs, or dairy consumption. These included questions on frequency of intake of oily fish, non-oily fish, processed meat, poultry, beef, lamb/mutton, pork, eggs, and dairy products. Questions on meat and fish were asked in the form of “how often do you eat [specific food or beverage?]” or similar. Valid options were 1 “never”, 2 “less than once a week”, 3 “once a week”, 4 “2-4 times a week”, 5 “5-6 times a week”, or 6 “once or more daily”. We will convert responses to these individual questions into weekly-based consumption frequencies as follows: 0, 0.5, 1, 3, 5.5, 7 servings/week.

We will sum responses to questions on intake of processed meat, poultry, beef, lamb/mutton, and pork to form total meat intake (servings/week); and questions on intake of oily and non-oily fish intake to form total fish intake (servings/week). Intake of eggs and dairy products was assessed by asking

participants “Which of the following do you never eat?”, with options of “Eggs or foods containing eggs”, “Dairy products”, “I eat all of the above”, or “Prefer not to answer”.

Diet groups will be regular meat-eaters (ate meat \geq 5 times/week), occasional meat-eaters (ate meat $<$ 5 times/week), pescatarians (reported never eating meat but ate fish), vegetarians (reported never eating meat or fish but did consume eggs or dairy products), and vegans (reported never eating meat, fish, eggs, or dairy products).

5.0 Outcomes

The primary outcome will be first incidence of hip fracture (ICD-9 code 820 and ICD-10 codes S72.0-S72.2) identified using hospital inpatient data for England, Scotland, and Wales. This includes Hospital Episode Statistics for England until 30th September 2021, Scottish Morbidity Records for Scotland until 31st July 2021, and the Patient Episode Database for Wales until 28th Feb 2018. The timeframe will be person-years until hip fracture incidence, or until end of study period or death in non-cases, calculated as age at time of event or censoring minus age at study entry. Sources and dates of availability for each region’s hospital inpatient data (and therefore censoring dates) are presented in Table 2.

Table 2: Hospital inpatient data in England, Scotland, and Wales.

Country	Data source	Period of time for which data is available
England	Hospital Episode Statistics (HES)	1997 – 30 th Sept 2021
Scotland	Scottish Morbidity Record (SMR)	1981 – 31 st July 2021
Wales	Patient Episode Database for Wales (PEDW)	1998 – 28 th Feb 2018

Adapted from: [External Info : Data providers and dates \(ox.ac.uk\)](#)

6.0 Sample size

The minimum detectable hazard ratio for potential associations between each diet group and hip fracture risk (with regular meat-eaters as the reference group) was estimated in Stata (v17.0) assuming the following parameters:

- Total sample size of 472,337 participants, including 247,571 regular meat-eaters, 205,385 occasional meat-eaters, 10,696 pescatarians, and 8685 vegetarians, as has been previously reported in a UK Biobank publication on risk of cancer in these diet groups (1). Numbers of participants in each diet group in our study may differ slightly to the cited UK Biobank study due to differences in exclusion criteria.

- Hip fracture incidence of 3%.
- $p < 0.05$.
- 80% power.
- A theoretical standard deviation of the exposure (diet group) calculated based on the percentage of participants in each diet group (Table 3).

Table 3: Minimal detectable hazard ratios for associations between diet groups and hip fracture risk with regular meat-eaters as the reference group.

Diet group	SD	Minimum detectable HR
Regular meat-eaters	Ref	Ref
Occasional meat-eaters	0.50	1.05
Pescatarians	0.20	1.17
Vegetarians	0.18	1.19
Vegans	0.04	1.82

SD = Standard deviation. HR = Hazard ratio. The SD for dietary group is theoretical and has arbitrary units.

7.0 Descriptive statistics

Dietary, lifestyle, socio-economic, anthropometric, and other relevant characteristics of the cohort at recruitment will be summarised using descriptive statistics (e.g. presenting their means and standard deviations) by diet group, in cases vs non-cases, and in men and women to report any differences in covariates (including co-exposures) between groups at recruitment.

8.0 Statistical modelling

8.1 Main analyses

8.1.1 Absolute risk difference

To estimate the population impact of being in each diet group on hip fracture incidence, we will determine the absolute risk difference for hip fracture between each diet group and regular meat-eaters (reference group) per 1000 people over 10 years. This will be calculated as the crude differences between the predicted incidence per 1000 people over 10 years between each diet group and the regular meat-eaters, using hazard ratios and 95% confidence intervals expressed as floating absolute risks, as described elsewhere (2).

8.1.2 Relative risk

Cox regression models will be applied to estimate HR (95% CI's) for associations between each diet group and hip fracture risk, with regular meat-eaters as the reference group. The proportional hazards assumption will be assessed based on Schoenfeld residuals.

8.1.3 Accounting for confounding

Unadjusted and adjusted cox models will be applied. Both will control for age by using attained age as the timescale. The adjustment set for the adjusted model will be informed by a DAG model, which will be constructed using the online tool DAGitty, following available guidelines on their use (3). Confounders will be considered as covariates that are 1) risk factors of the outcome; 2) associated with the exposure; and 3) not on the causal pathway (4). Potential confounders are age at recruitment, sex, region, ethnicity, socio-economic status or education, marriage, physical activity, smoking, alcohol, BMI (or height and weight), number of children, menopausal status, hormone replacement therapy (HRT) in postmenopausal women, chronic disease prevalence at recruitment, and use of nutritional supplements (either generic or supplement-specific e.g. for calcium, vitamin D, and fish oil in particular, depending on availability of data). A list of likely confounders and their derivation is summarised in Supplementary Table 1.

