8.3 Mediation analyses

If a significant association is observed between any diet group and hip fracture in the main analysis (with regular meat-eaters as the reference group), we will further explore the potential mediating

effect of variables that have previously been associated with – or could plausibly be associated with – diet groups and hip fracture risk. Potential mediators include (all measured at recruitment):

- Potential anthropometric mediators: BMI, BMD (at the heel and femoral neck depending on availability of data and number of participants with each measure), bone mineral content, lean muscle mass, hand grip strength, and fat mass;
- Circulating vitamin D and IGF-1 levels;
- Total energy intake and dietary intake of protein, calcium, vitamin B12, and omega-3' fatty acids.

For each potential mediator, we will explore whether it is more appropriate to use measures at recruitment (extrapolated to represent measures during the study period), or to calculate changes in the mediator variable of interest from recruitment to the latest measurement during follow-up, depending on the availability of mediator data in UK biobank participants.

To determine if each of the potential mediators listed vary by diet group, multiple linear regression will be used, adjusting for relevant confounders. We will not explore mediation if there is no significant difference in risk of hip fracture across diet groups, or if the mediator is not significantly different between each diet group and regular meat-eaters.

We will test for mediation using the inverse odds ratio weighting (IORW) method, which estimates the natural direct and indirect effects of potential mediators, and is described in detail elsewhere (5-7).

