8.4 Sensitivity analyses

1. An adjusted model with BMI removed from the adjustment set will be presented to determine the contribution of weight management to any associations.
2. We will present an adjusted model with vegans and vegetarians separated to determine if excluding vegans from the vegetarian group alters potential associations with hip fracture risk.
3. Online follow-up 24-hour dietary recall data will be compared with touchscreen FFQ data at recruitment to check for changes in diet group over time. In cases of substantial exposure change over time (e.g., > 10% of participants changing their dietary group), models will be repeated restricted to participants who maintained their original diet group.
4. Excluding cases occurring in the first three years of follow-up to check for reverse causality.
5. Excluding participants on long-term treatment for illnesses at recruitment who may be generally unhealthier and therefore at a higher risk of hip fracture.

6. We will explore patterns of missing covariate data, and will use multiple imputation through Stata's 'mi' package in the event of substantial missing covariate data.

All analyses will be performed using Stata. Two-sided p values < 0.05 will be considered statistically significant. All analyses performed and effect sizes computed will be presented in resulting manuscripts to avoid bias in selection of the reported result.

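### BMI is both confounder and mediator, and neither the mediation gate nor the risk difference names its model; on the plain reading, the BMI-mediation gate tests an effect with BMI held fixed

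*SAP*

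**What the plan says.** - **BMI as confounder.** SAP Section 8.1.3 sets three conditions for a confounder, the last two being "2) associated with the exposure; and 3) not on the causal pathway". Its list of potential confounders then includes "marriage, physical activity, smoking, alcohol, BMI (or height and weight"). The final set is to be informed by a DAG. Unadjusted and adjusted Cox models are planned, both with attained age as the timescale.
- **BMI as mediator.** Section 1.2 sets a secondary objective on mediation, "including the roles of BMI, measures of body composition measures, circulating levels of vitamin D and IGF-1" and dietary intakes. Section 8.3 repeats it: "Potential anthropometric mediators: BMI, BMD (at the heel and femoral neck" and so on, followed by lean mass and fat mass among others.
- **The gate.** Section 8.3 starts mediation work "If a significant association is observed between any diet group and hip fracture in the main analysis". It also states the reverse: "We will not explore mediation if there is no significant difference in risk of hip fracture across diet groups". Neither sentence says which Cox model decides.
- **Mediator regressions.** Section 8.3 says that "multiple linear regression will be used, adjusting for relevant confounders". It does not say whether BMI is one of those confounders when the mediator is BMI, fat mass or lean mass.
- **The model without BMI.** Section 8.4, item 1: "An adjusted model with BMI removed from the adjustment set will be presented", to show what weight management contributes.
- **Risk difference.** Section 8.1.1 derives the difference per 1000 people over 10 years, described as a population impact, from hazard ratios. It does not name the model that supplies them.

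**The concern.** Under the SAP's own third condition, a variable on the pathway does not belong in the adjustment set of a model meant to give the total effect of diet group. BMI can be removed in sensitivity analysis 1 only if it was there before. So the one confounder-adjusted model that keeps the BMI pathway is a sensitivity analysis, and neither the gate nor the risk difference refers to it.

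Four things are at stake:

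1. **Same direction.** If the BMI pathway and the rest of the diet effect point the same way, a gate on the BMI-adjusted hazard ratio is least likely to open when BMI explains most of the effect. A stated secondary objective could be dropped for the wrong reason.
2. **Opposite direction.** If they point in opposite ways, the gate opens more readily than the total effect warrants.
3. **Risk difference.** A population-impact figure built from the BMI-adjusted hazard ratio would leave out any BMI pathway without saying so.
4. **Mediator models.** If BMI at recruitment stayed as a covariate while it was also the mediator, its indirect effect could not be estimated.

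**Working it through.** **Step 1. Reproduce Table 3.** Inputs from SAP Section 6.0: 247,571 regular meat-eaters, 205,385 occasional meat-eaters, 10,696 pescatarians, 8,685 vegetarians; hip fracture incidence 3%; p < 0.05 (two-sided, Section 8.4); 80% power. SD = [p(1 − p)]^0.5 is from Fig S1. Each group is taken pairwise with regular meat-eaters:

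ln HR = (1.960 + 0.842) / (SD × √events), with events = 3% of the two groups together.

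| Group | p | SD | Events | ln HR | HR | Table 3 |
|---|---|---|---|---|---|---|
| Occasional meat-eaters | 0.453 | 0.498 | 13,589 | 0.0483 | 1.05 | 1.05 |
| Pescatarians | 0.041 | 0.199 | 7,748 | 0.160 | 1.17 | 1.17 |
| Vegetarians | 0.034 | 0.181 | 7,688 | 0.177 | 1.19 | 1.19 |

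All three rows agree with the plan.

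**Step 2. Power of one comparison with BMI held fixed.** Let f be the share of the total ln HR that runs through BMI. The SAP gives no value, so f is varied. Take the total effect at the Table 3 HR and leave the standard error unchanged. The expected z is then 2.802 × (1 − f), and power is Φ(z − 1.960) + Φ(−z − 1.960).

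| f | Expected z | Power | HR tested, vegetarians |
|---|---|---|---|
| 0 | 2.802 | 80% | 1.19 |
| 0.25 | 2.101 | 56% | 1.14 |
| 0.50 | 1.401 | 29% | 1.09 |
| 0.75 | 0.700 | 11% | 1.05 |
| −0.25 (opposite direction) | 3.502 | 94% | not shown |

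Starting from the rounded HR of 1.19 for vegetarians gives 79%, 54%, 28% and 11% for f = 0 to 0.75, which is the same picture.

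**Step 3. The gate as written.** It opens if any diet group differs significantly. Treat it as three two-sided 5% tests that share a reference group. With d = 3% of group size, each ln HR has variance 1/d_group + 1/d_ref, and any two have covariance 1/d_ref. From 1,000,000 simulated trivariate normal draws:

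| f | All three groups at the Table 3 HR | Vegetarians only |
|---|---|---|
| 0 | 99% | 82% |
| 0.25 | 89% | 60% |
| 0.50 | 62% | 36% |
| 0.75 | 28% | 19% |

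With no effect left in any group, the gate still opens 14% of the time, which is the floor set by three 5% tests.

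**Step 4. What does not depend on these numbers.** The two roles given to BMI, and the unnamed model in Sections 8.1.1 and 8.3, follow from the text alone. The arithmetic only shows how much the choice of model can matter.

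**The case against.** - **The lists are provisional.** Section 8.1.3 speaks of potential confounders and leaves the set to a DAG; Section 8.3 speaks of potential mediators. BMI and diet are both measured at recruitment, so BMI may well be part confounder. This stands as a reason to keep a BMI-adjusted model. It does not settle which model drives the gate, and sensitivity analysis 1 already presumes that BMI is in the set.
- **The authors foresaw the issue.** The model without BMI is planned, and Section 8.4 commits to presenting all analyses. Readers will see both hazard ratios, so part of the remedy is only labelling. But nothing links that model to the gate or to the risk difference.
- **The main analysis might mean something else.** Section 8.1 covers the unadjusted model too, and that model does not hold BMI fixed. The consequence for the gate is therefore conditional. The adjusted model is the plain reading, and an unadjusted gate would ignore every confounder except age.
- **One gate serves many mediators.** Most of them, such as vitamin D, IGF-1 and the nutrient intakes, are not measures of body size, and no case is made here that a BMI-adjusted gate is wrong for those. The point is limited to BMI and body composition.
- **Relevant confounders already excludes BMI when BMI is the mediator.** That is a fair reading for BMI itself. It is much less clear for fat mass and lean mass.
- **Section 8.1.1 follows a cited source.** That source is not at hand and may settle the model; the SAP itself does not.
- **The illustration is favourable to the concern.** It sets the total effect exactly at the detectable limit, assumes the BMI share and holds the standard error fixed. With effects in all three groups and a 25% share, the gate still opens 89% of the time. The large losses need shares of 50% to 75%.

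**Conclusion.** The concern holds and should be fixed. The SAP gives BMI two roles that its own definition of a confounder does not allow in one total-effect model, and it leaves unnamed the model behind two results that depend on the choice. On the plain reading, the gate for BMI mediation tests the wrong quantity for that question.

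The size depends on a BMI share that the documents do not give. For a total effect at the Table 3 limits, power for a single comparison falls from 80% to between 56% and 11% as a same-direction share rises from 25% to 75%. An opposite share of 25% raises it to 94%. For the gate as a whole, the chance of opening falls from 99% to between 89% and 28% if all three groups have an effect, and from 82% to between 60% and 19% if only vegetarians do. These figures assume an unchanged standard error. Confidence is high in the textual inconsistency and the missing specification; the loss itself is illustrative.

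**What to change.** 1. **Section 8.1.3 and Section 8.4, item 1:** keep both planned adjusted models and label what each estimates. Without BMI: the effect including the BMI pathway (total effect). With BMI: the effect not through BMI.
2. **Section 8.3, gate:** base the decision for BMI and body-composition mediators on the adjusted model without BMI.
3. **Section 8.1.1:** name the model. Report the absolute risk difference from the adjusted model without BMI beside the BMI-adjusted one, each labelled.
4. **Section 8.3, mediator models:** state that BMI (or weight, if used in its place) is not a covariate in the mediator regression or the IORW models when BMI, fat mass or lean mass at recruitment is the mediator. Height may stay.

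The cost is a few sentences and one extra risk-difference column, since both models are already planned and no new data are needed. The downside is that any BMI difference that preceded the choice of diet is left unadjusted in the total-effect model. The documents do not allow that bias to be sized, but showing the two models side by side discloses it.
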